8.2 Definitions of DLT

Toxicity will be evaluated according to the NCI CTCAE, Version 5.0.

Nonhematologic TEAEs of NCI CTCAE Grade ≥ 3 clearly unrelated to the underlying disease and occurring during the first cycle will be considered DLTs (see Section 10.2 for relatedness guidance), with the following exceptions:

- Asymptomatic laboratory changes (other than renal and hepatic laboratory values, and Grade 4 lipase/amylase) that can be successfully supplemented (reversion of Grade 4 events to Grade ≤2, reversion of Grade 3 events to Grade ≤1 or baseline) within 72 hours.
- Grade 3 nausea/vomiting that can be managed subsequently with antiemetics (Grade 3 nausea or vomiting that persists beyond 48 hours with or without appropriate medical intervention will be considered a DLT).
- Grade 3 fatigue lasting less than 72 hours.
- Grade 3 elevation of alanine aminotransferase (ALT) or aspartate aminotransferase (AST) that resolves to Grade ≤1 or baseline within 7 days.
- Grade 3 IRR that responds to symptomatic treatment, without recurrence of Grade 3 symptoms.

The following hematologic TEAEs Grade ≥3 clearly unrelated to the underlying disease and occurring during the first cycle will be considered DLTs:

- Grade \geq 3 hemolysis.
- Grade 4 neutropenia lasting more than 7 consecutive days.
- Grade 4 thrombocytopenia lasting more than 14 consecutive days.
- Grade 3 thrombocytopenia with clinically significant bleeding.
- Any other Grade ≥4 hematologic toxicity with the exception of Grade 4 lymphopenia.

An incomplete recovery from treatment-related toxicity causing a >2-week delay in the next scheduled infusion before the initiation of Cycle 2 will be considered a DLT.

In Part 1, DLTs are events meeting the criteria above that occur before Cycle 2 Day 1 administration. Related TEAEs meeting DLT definitions occurring in later cycles or in Phase 2 (DLT-like events) will determine the suitability of the MTD/OBD dose for future studies.

Dose and schedule modifications for toxicity are described in Section 8.4.

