10.0 ADVERSE EVENTS

10.1 Definitions

10.1.1 Pretreatment Event Definition

A pretreatment event is any untoward medical occurrence in a patient or subject who has signed informed consent to participate in a study but before administration of any study medication; it does not necessarily have to have a causal relationship with study participation.

10.1.2 **AE Definition**

AE means any untoward medical occurrence in a patient or subject administered a pharmaceutical product; the untoward medical occurrence does not necessarily have a causal relationship with this treatment. An AE can therefore be any unfavorable and unintended sign (including an abnormal laboratory finding), symptom, or disease temporally associated with the use of a medicinal (investigational) product whether or not it is related to the medicinal product. This includes any newly occurring event, or a previous condition that has increased in severity or frequency since the administration of study drug.

An abnormal laboratory value will not be assessed as an AE unless that value leads to discontinuation or delay in treatment, dose modification, therapeutic intervention, or is considered by the investigator to be a clinically significant change from baseline.

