Appendix C Algorithms of DLT-like Events

Wording from Protocol Section 8.2	Programmatic algorithm

1) Nonhematologic TEAEs of NCI CTCAE Grade ≥ 3 clearly unrelated to the underlying disease and occurring during the first cycle will be considered DLTs (see Section 10.2 for relatedness guidance), with the following exceptions:
	
For DLT-like events from AE data, check for Grade 3 or higher drug-related nonhematologic TEAEs, i.e. AEs with AETOXGR in (“GRADE 3” “GRADE 4” “GRADE 5”) and AEREL=“RELATED”, then remove the exceptions from 1b to 1e
 
For nonhematologic DLT-like events from laboratory data see instructions in 1a.

a. Asymptomatic laboratory changes (other than renal and hepatic laboratory values, and Grade 4 lipase/amylase) that can be successfully supplemented (reversion of Grade 4 events to Grade ≤ 2, reversion of Grade 3 events to Grade ≤ 1 or baseline) within 72 hours.
	
1) Pull out any Grade 3 or higher renal and hepatic chemistry lab values i.e. where LBTOXGR in (“GRADE 3” “GRADE 4” “GRADE 5”) and LBTESTCD in (“CREAT” “BUN” “BILI” “ALT” “AST”). All Grade 3 or higher results are considered DLT-like events.
 
2) Pull out any Grade 3 or higher chemistry lab values not included in point 1, i.e. where LBTOXGR in (“GRADE 3” “GRADE 4” “GRADE 5”) and LBCAT=“CHEMISTRY” and LBTESTCD not in (“CREAT” “BUN” “BILI” “ALT” “AST”), and keep the records that don’t return to baseline (or go from Grade 3 to 1, or from grade 4 to 2) within 3 days.
 
These results are considered DLT-like events.
 
Note:
 
 • Exclude pre-existing abnormalities, e.g. if a patient has Grade 3 ALT at baseline and post-baseline, this is not considered a DLT-like event since the abnormality was present at baseline. • Renal includes: creatinine, blood urea nitrogen • Hepatic includes: bilirubin, ALT, AST • Lipase and amylase are not collected

b. Grade 3 nausea/vomiting that can be managed subsequently with anti-emetics (Grade 3 nausea or vomiting that persists
	
AEDECOD in (“Nausea” “Vomiting”) and AETOXGR in (“GRADE 3”) and AEDUR ≤ 2

beyond 48 hours with or without appropriate medical intervention will be considered a DLT).
	

c. Grade 3 fatigue lasting less than 72 hours.
	
AEDECOD in (“Fatigue”) and AETOXGR in (“GRADE 3”) and AEDUR <= 3

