
d. Grade 3 elevation of ALT or AST that resolves to Grade ≤1 or baseline within 7 days.
	
AEDECOD in (“Alanine aminotransferase increased” “Aspartate aminotransferase increased”) and AETOXGR in (“GRADE 3”) and AEDUR <=7 and AEOUT=“RECOVERED/RESOLVED”

e. Grade 3 IRR that responds to symptomatic treatment, without recurrence of Grade 3 symptoms.
	
IRRFL=“Y” and AETOXGR in (“GRADE 3”) Note: IRR events and signs and symptoms are considered for this.

2) The following hematologic TEAEs of Grade ≥3 clearly unrelated to the underlying disease and occurring during the first cycle will be considered DLTs:
	
For DLT-like events from AE data, check for drug-related hematologic TEAEs then search for the following event in 2a. For hematologic DLT-like events from laboratory data see instructions in 2e.

a. Grade ≥3 hemolysis.
	
AEDECOD in (“Hemolysis”) and AETOXGR in (“GRADE 3” “GRADE 4” “GRADE 5”)

b. Grade 4 neutropenia lasting more than 7 consecutive days
	
N/A – see 2e.

c. Grade 4 thrombocytopenia lasting more than 14 consecutive days.
	
N/A – see 2e.

d. Grade 3 thrombocytopenia with clinically significant bleeding.
	
N/A – see 2e.

e. Any other Grade ≥4 hematologic toxicity with the following exception:
 
a. Grade 4 lymphopenia
	
Check for Grade 4 or higher hematology lab values, except lymphocytes per the exclusion note i.e. LBTOXGR in (“GRADE 4” “GRADE 5”) and LBCAT=“HEMATOLOGY” and LBTESTCD not in (“LYM”). Apply the following to the remaining parameters:
 
 1) For all parameters except platelets and neutrophils i.e. LBTESTCD not in (“NEUT” “PLAT”), any occurrence of a Grade 4 or higher result will be considered a DLT-like event. 2) For platelets and neutrophils, i.e. where LB.LBTESTCD in (“NEUT” “PLAT”),

	
keep the record if the patient's result doesn't return to the following prior to or including the next scheduled dose date (use exposure dates for this):
 
Platelets $\geq 50 \text{ } 10^9/\text{L}$ Neutrophils $\geq 1 \text{ } 10^9/\text{L}$
 
Scheduled dose date = date the next dose should have occurred, e.g. schedule D would be 28 days after the previous dose.

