3) An incomplete recovery from treatment-related toxicity causing a >2 -week delay in the next scheduled infusion before the initiation of Cycle 2 (or next cycle if after cycle 1) will be considered a DLT.	Any TEAEs with AEREL="RELATED" and AEACN="DOSE DELAYED" and the next dose was delayed for >14 days

Assumptions:

- 1) Hematologic AEs include the following PTs:

Hematology collection from protocol	Preferred term
Hematocrit	“Anaemia” “Hemolysis”
Hemoglobin	“Anaemia” “Hemolysis”
Leukocytes with differential	“Leukopenia” “White blood cell count decreased”
Neutrophils (ANC)	“Neutropenia” “Neutrophil count decreased” “Febrile neutropenia”
Platelet (count)	“Thrombocytopenia” “Platelet count decreased”
Lymphocytes	“Lymphopenia” “Lymphocyte count decreased”

Note: PTs may change with coding updates.

- 2) Only include TEAEs which are related to study drug.
- 3) Duration is calculated in days, not hours e.g. 48 hours = 2 days (This would check the day of AE and the next day).
- 4) For 'Clinically significant bleeding', this is included in the non-hematologic AE part. Considering 'clinically significant' as Grade 3 or higher. No need to check for the thrombocytopenia, that is checked via the laboratory data.

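### SAP Appendix C does not implement the Protocol 8.2 definition of DLT-like events: laboratory values count with no relatedness test, and exempt transient changes are counted

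*SAP*

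**What the plan says.** Protocol 8.2 sets the definition and the use: "Related TEAEs meeting DLT definitions occurring in later cycles or in Phase 2 (DLT-like events) will determine the suitability of the MTD/OBD dose". The DLT criteria it refers to require events that are clearly not due to the underlying disease. They exempt, among others, asymptomatic laboratory changes other than renal and hepatic values that are corrected within 72 hours (exception a), and Grade 3 ALT/AST rises that resolve within 7 days (item 1d in the SAP, called exception d here). Protocol 10.1.2 adds that a laboratory value is not automatically an AE: "An abnormal laboratory value will not be assessed as an AE unless that value leads to discontinuation or delay in treatment", with a few further triggers.

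SAP Section 7.12.1 says DLT-like events after Cycle 1 in Parts 1 and 2 are identified programmatically, then summarized and listed. Appendix C gives the algorithm:

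- AE route, item 1: "check for Grade 3 or higher drug-related nonhematologic TEAEs", with AEREL set to related, "then remove the exceptions from 1b to 1e".
- Laboratory route, item 1a point 1 (creatinine, BUN, bilirubin, ALT, AST): "All Grade 3 or higher results are considered DLT-like events".
- Laboratory route, item 1a point 2 (other chemistry): Grade 3 or higher records are kept if they do not "return to baseline (or go from Grade 3 to 1, or from grade 4 to 2) within 3 days".
- Laboratory route, item 2e, hematology other than lymphocytes, platelets and neutrophils: "any occurrence of a Grade 4 or higher result will be considered a DLT-like event". Platelets and neutrophils are judged on recovery by the next scheduled dose date.

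Assumption 2 reads "Only include TEAEs which are related to study drug". Item 1a also excludes abnormalities already present at baseline.

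**The concern.** The two routes apply different definitions. The AE route asks whether the event was related; the laboratory route does not. The Protocol's own Appendix F links some of these analytes to the disease: renal insufficiency is a myeloma-defining event, and hypercalcemia attributable solely to the plasma cell disorder is a progression criterion. Calcium is in the chemistry panel (Protocol Table 9.a). A patient who progresses can therefore be scored with drug toxicity because of the progression.

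The exemptions are also applied unevenly, so an event removed by one route can return through the other. At stake is a stated secondary endpoint in Parts 1 and 2, which Protocol 8.2 says informs whether the MTD/OBD is suitable. A count that includes disease effects can rise with follow-up and with progression, and both may differ between cohorts.

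**Working it through.** The plan gives no figure to reproduce, since this is a derivation rule. The check sets the routes against the Protocol and then tests the 3-day rule against the visit schedule.

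**1. Hypothetical records after Cycle 1, followed through the rules as written**

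| Record | Protocol 8.2 | AE route | Laboratory route |
|---|---|---|---|
| New Grade 3 creatinine, attributed to progression | Not DLT-like | Not counted (not related) | Counted, 1a point 1 |
| Related Grade 3 ALT rise, resolved by day 5 | Exempt (exception d) | Removed by 1d | Counted, 1a point 1 |
| Related asymptomatic Grade 3 non-renal, non-hepatic laboratory AE, corrected and retested within 72 hours | Exempt (exception a) | Counted; only 1b to 1e are removed | Not counted, recovery shown |
| The same abnormality, no retest within 3 days | Exemption not established | Counted if recorded as a related AE | Kept, 1a point 2 |
| New Grade 4 leukocyte value judged unrelated | Not DLT-like | Not counted | Counted, 2e |

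Assumption 2 does not rescue the laboratory column. It is worded for TEAEs, and the laboratory selections use only grade, category and test code. The baseline exclusion removes old abnormalities, not new ones arising on study.

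**2. Can recovery within 3 days be observed?**

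Inputs are the chemistry rows and visit windows in Protocol Appendix A for Schedules A to D, from C2D1 to Cycle 13. Shortest possible gap = nominal gap − window of the earlier visit − window of the later visit.

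- Cycle 2, all schedules: 7 − 2 − 2 = 3 days.
- From Cycle 3: A, 14 − 2 − 4 = 8 (C6D15 to C7D1); B, 14 − 2 − 2 = 10; C, 21 − 4 − 4 = 13; D, 28 − 4 − 4 = 20.

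| Schedule | Smallest nominal gap, Cycle 2 | With windows | Smallest nominal gap, Cycle 3 on | With windows | Nominal gaps of 3 days or less |
|---|---|---|---|---|---|
| A | 7 | 3 | 14 | 8 | 0 of 18 |
| B | 7 | 3 | 14 | 10 | 0 of 25 |
| C | 7 | 3 | 21 | 13 | 0 of 13 |
| D | 7 | 3 | 28 | 20 | 0 of 14 |

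A 3-day gap therefore arises between scheduled visits only in Cycle 2, and only when both visits fall at opposite window extremes. Assumption 3 counts days inclusively (48 hours is the event day and the next day). If that convention also governs the laboratory check, even a 3-day gap falls outside it. Appendix C does not say what to do when there is no retest; read literally, the record is kept.

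**3. Size**

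The documents give no rate of disease-caused or transient Grade 3 or higher values, so no expected inflation can be computed. In a Part 2 cohort of 25, each patient counted only through these routes adds 1/25 = 4 percentage points.

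**The case against.** Several points on the other side stand.

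- **Renal and hepatic values.** Exception a expressly leaves these out, so giving creatinine, BUN and bilirubin no 72-hour reprieve follows the Protocol. A reader might take the quoted renal/hepatic sentence as the 3-day problem. It is not: that sentence has no recovery check, and its faults are the missing relatedness test and the clash with 1d on ALT/AST.
- **The schedule.** A reader might infer that the 3-day check can never be met. That goes too far. Unscheduled draws are allowed at the investigator's discretion (Protocol 9.3.9.6), and re-evaluation is at least weekly while a dose is withheld (Protocol 8.4.3). A sentence in 9.3.9.6, placed with the Part 3 text, allows panels up to 3 days before dosing; if it also applied to Parts 1 and 2 it could shorten some gaps. Recovery can rarely be shown from scheduled visits, which is a weaker statement.
- **Relatedness in the endpoint.** The word appears in Protocol 8.2, not in the endpoint lists, which say only TEAEs meeting the DLT definition. The conflict remains, because that definition sits in 8.2 and the laboratory route requires no TEAE at all.
- **Using laboratory data is deliberate and cautious.** In a first-in-human study, ignoring severe values that sites did not report would be a poor remedy, and treating a missing retest as recovery would read missing data as no toxicity. This bears on the fix, not on the finding.
- **Other outputs exist.** Drug-related TEAE tables and a by-patient DLT-like listing permit case review. They limit the harm but do not correct the summarized rate.

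**Conclusion.** Wrong as written. For Parts 1 and 2 after Cycle 1, Appendix C departs from Protocol 8.2 in four ways: no relatedness link in 1a and 2e; re-counting of exempt Grade 3 ALT/AST rises; no use of exception a in the AE route; and a 3-day recovery test that scheduled visits can rarely satisfy, with retention by default. The first three follow from the text alone. The fourth assumes that no unscheduled draw was taken.

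The direction is over-counting; the amount cannot be stated from the documents.

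A reader might infer that the MTD, the 40% stopping threshold in Protocol 8.3 or the Part 3 results are compromised. The documents do not support that. Cycle 1 DLTs are identified by the investigator, the 3 mg/kg Q4W MTD is already established, the programmatic count covers Parts 1 and 2 only, and nothing says it feeds the 40% rule. The effect is confined to the descriptive DLT-like summary, which should still be corrected before it is used to judge dose suitability.

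**What to change.** Amend SAP Appendix C as follows.

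1. In 1a and 2e, count a laboratory record as a DLT-like event only when it matches a TEAE with AEREL='RELATED' for the same parameter and overlapping dates. Tabulate unmatched Grade 3 or higher (1a) and Grade 4 or higher (2e) records separately as 'laboratory, unattributed'.
2. Apply exception d to ALT/AST in 1a, so that a Grade 3 rise removed by 1d is not counted again.
3. Apply exception a to laboratory abnormalities in the AE route, keeping its exclusion of renal and hepatic values.
4. Where there is no repeat value within 3 days (7 days for ALT/AST under exception d), use the matched AE's dates and outcome. If these do not settle it, report the event in a 'recovery not assessed' row and give the rate with and without that row. Do not drop it.

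The cost is SAP wording and a merge of the laboratory and AE datasets; no new data are needed. The downside is that severe values never reported as AEs move from the headline count to a separate category, where they remain visible.

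### SAP Appendix C item 2 does not fully implement the Protocol 8.2 residual category of Grade ≥4 hematologic toxicity, so some hematologic AEs can go unflagged as DLT-like events in Parts 1 and 2

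*SAP*

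**What the plan says.** Protocol 8.2 lists specific hematologic DLTs: hemolysis, neutropenia and thrombocytopenia with duration conditions, and thrombocytopenia with bleeding. It then adds a residual category, "Any other Grade ≥4 hematologic toxicity with the exception of Grade 4 lymphopenia". It is not restricted to laboratory findings. The same section gives later events their purpose: "Related TEAEs meeting DLT definitions occurring in later cycles or in Phase 2 (DLT-like events) will determine the suitability of the MTD/OBD dose".

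SAP Section 7.12.1 says that DLT-like events after Cycle 1 in Part 1, and in Part 2, are identified programmatically by Appendix C. The relevant parts of Appendix C are:

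- **Item 1** searches AE data for related Grade ≥3 nonhematologic TEAEs.
- **Assumption 1** ("Hematologic AEs include the following PTs") lists anaemia, leukopenia, neutropenia, febrile neutropenia, thrombocytopenia and lymphopenia terms, plus hemolysis.
- **Item 2, AE data:** "For DLT-like events from AE data, check for drug-related hematologic TEAEs then search for the following event in 2a". Row 2a is "Grade ≥3 hemolysis".
- **Item 2, laboratory data:** "For hematologic DLT-like events from laboratory data see instructions in 2e". Rows 2b to 2d are marked not applicable and refer to 2e.
- **Row 2e:** "Check for Grade 4 or higher hematology lab values, except lymphocytes per the exclusion note". Neutrophils and platelets carry a further condition: "keep the record if the patient's result doesn't return to the following prior to or including the next scheduled dose date".
- **Item 3** flags any related TEAE with a dose delay when the next dose is more than 14 days late.

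**The concern.** The residual category is defined by toxicity grade, but the program reads it only from laboratory grades. Classing a term as hematologic takes it out of the item 1 AE search, and item 2 then offers an AE search for hemolysis alone.

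Febrile neutropenia is not a laboratory test, and none is listed for it in Protocol Table 9.a. A fatal grade, or a life-threatening grade given on clinical grounds, does not come from a count. Assumption 4 sends clinically significant bleeding to the AE route, so the authors did provide for a clinical consequence of a low count in that case. Febrile neutropenia has no such route, and no reason is given.

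DLT-like frequency is a named secondary endpoint in Parts 1 and 2. The drug's main toxicity is hematologic: Protocol 4.6.2 reports neutropenia in 70% of patients (30% Grade 4) and thrombocytopenia in 73% (17% Grade 4). A count that departs from its own protocol definition in this class of toxicity is a poor basis for judging the MTD/OBD.

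**Working it through.** The plan states no figure to reproduce. The check is a trace of hypothetical related events through the rules as written.

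**Step 1, terms with an AE search.** Assumption 1 lists anaemia (1), hemolysis (1), leukopenia and white cell count decreased (2), three neutrophil terms including febrile neutropenia (3), two platelet terms (2) and two lymphocyte terms (2). The total is 1 + 1 + 2 + 3 + 2 + 2 = 11. Item 2 searches AE data for one of them, hemolysis, which leaves 11 − 1 = 10 without a search.

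**Step 2, trace.** All events are related, with no delay over 14 days unless stated and no laboratory record other than the one shown.

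| Event | Route that flags it |
|---|---|
| Grade 4 febrile neutropenia; Grade 4 neutrophils, recovered by next scheduled dose | none |
| Grade 4 febrile neutropenia; lowest recorded neutrophils Grade 3 | none |
| Grade 5 febrile neutropenia; no Grade 4 neutrophil record | none |
| Grade 5 thrombocytopenia AE; no laboratory record | none |
| Grade 4 anaemia AE; hemoglobin Grade 3 | none |
| Grade 4 leukopenia AE; no laboratory record | none |
| Grade 5 lymphopenia (2e drops lymphocytes at every grade) | none |
| Grade 4 or 5 febrile neutropenia; Grade 4 neutrophils not recovered | 2e |
| Grade 4 leukopenia; Grade 4 white cell value | 2e |
| Grade 4 anaemia; next dose 21 days late | item 3 |
| Grade 4 hemolysis | 2a |
| Grade 4 pancytopenia (not on the list) | item 1 |

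The first seven rows meet the residual category, taking febrile neutropenia as other than plain neutropenia, and none is flagged. These are constructed cases. They show that the gap exists, not how often it occurs.

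**Step 3, what the other routes cover.** Row 2e flags any Grade 4 value for a parameter other than neutrophils, platelets and lymphocytes, with no recovery condition. A febrile neutropenia accompanied by a Grade 4 white cell value is therefore caught even if neutrophils recover. Item 3 catches a related AE followed by a long delay, but it needs a next dose and so cannot catch a fatal event.

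**Step 4, how far laboratory data can stand in.** From Cycle 3, Schedules C and D plan hematology on Day 1 only (Appendix A Tables 7, 8 and 10), and Protocol 8.4.2 lets G-CSF be used to reach the neutrophil level for a new cycle. On the other side, Cycle 2 has intermediate draws, Protocol 8.4.3 requires at least weekly re-evaluation when a dose is withheld, and 9.3.9.6 allows extra local tests. Coverage is partial in both directions.

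**The case against.** The strongest reply is that the residue is small and largely a matter of labels. Much of this stands.

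- **The residual category covers only other toxicities.** Grade 4 neutropenia and thrombocytopenia have their own duration rules (more than 7 and more than 14 days), so leaving short episodes unflagged is correct. Four of the 10 unsearched terms are plain neutrophil or platelet terms, and two are lymphocyte terms, exempt at Grade 4. Anaemia and leukopenia will usually have a laboratory value that 2e reads.
- **Febrile neutropenia is not named in Protocol 8.2.** Appendix C groups it with neutrophils, so someone could argue that the 7-day rule governs it. Neither document says so, and that reading would not deal with Grade 5 events.
- **Little turns on it for dose escalation.** Cycle 1 DLTs are identified by the investigator, and only those influenced escalation. The MTD has already been established, and the Part 3 dose choice rests on the totality of data.

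A reader might also infer more than the documents support:

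- *That an unrecovered Grade 4 neutrophil value is the sole safeguard for febrile neutropenia.* It is not: a Grade 4 white cell value and item 3 are further routes.
- *That these events leave the secondary endpoint altogether.* The endpoint also covers other TEAEs. SAP 7.12.1 tabulates Grade 3–4, serious, Grade 5 and drug-related Grade 5 events and lists every death.
- *That the DLT-like rate is biased low overall, and more so at higher doses.* This omission can only lower the count, but other rules can raise it. Item 1a flags every new Grade ≥3 ALT or AST laboratory value, whereas Protocol 8.2 exempts Grade 3 elevations that resolve within 7 days. The net direction is unknown, and no dose trend can be derived.
- *That a percentage can be attached.* In a 25-patient cohort each missed patient is 1/25 = 4 percentage points, but the documents give no febrile neutropenia rate and no number of missed patients, which could be zero.

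**Conclusion.** The point holds in a limited form and should be corrected. Followed exactly, Appendix C does not implement the protocol category that it quotes. Related Grade 4–5 febrile neutropenia, Grade 5 hematologic AEs, and hematologic AEs without a matching Grade ≥4 laboratory record can miss the DLT-like flag unless 2e or item 3 happens to apply.

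The effect is confined to the DLT-like count in Parts 1 and 2, and its size cannot be computed from the documents. The conclusion assumes that the program follows the written rule and, for febrile neutropenia at Grade 4, that the event belongs to the residual category. The Grade 5 and unmatched-grade gaps do not depend on that second assumption.

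**What to change.** Add an AE-data search to Appendix C row 2e: `AEREL` = RELATED, `AEDECOD` in the Assumption 1 hematologic list, and `AETOXGR` Grade 4 or 5, excluding lymphopenia and lymphocyte count decreased at Grade 4. For Grade 4 neutropenia and thrombocytopenia terms, keep the existing Protocol 8.2 duration conditions, so that short episodes are not newly counted. State that febrile neutropenia falls under the residual category, so that Appendix C and Protocol 8.2 are reconciled. De-duplicate against the laboratory route by patient and episode.

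The cost is a few lines of SAP text and minor programming on data already collected. The reported DLT-like rate may rise slightly.

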8.7.1.1.2 Grade 3 or Higher IRRs

The recommendations for managing Grade ≥3 IRRs are presented in Table 8.h.

Table 8.h Recommendations for Managing Grade ≥3 IRRs

IRR	Action
Any Grade 4 event	Patient must be withdrawn from treatment.
Grade 3 bronchospasm or laryngeal edema	Patient must be withdrawn from treatment.
Grade 3 event other than bronchospasm or laryngeal edema	Infusion must be stopped, and the patient must be observed carefully until resolution of the IRR.
If the intensity of the IRR remains at Grade 3 after 2 hours:	Patient must be withdrawn from treatment.
If the intensity of the IRR decreases to Grades 1 or 2:	Infusion may be restarted at the investigator's discretion. Administer corticosteroids, acetaminophen, and antihistamines per Sections 8.6.1 and 8.6.2 before restarting infusion. Within 2 hours upon restart, the infusion rate should be half of that employed before the interruption. Subsequently, the infusion rate may be increased at the investigator's discretion.
If the intensity of the IRR returns to Grade 3:	The procedure described above may be repeated after restart of the infusion at the investigator's discretion.
If the intensity of the IRR increases to Grade 3 for a third time:	Patient must be withdrawn from treatment.

IRR: infusion-related reaction.

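### SAP Appendix C departs from the Protocol 8.2 DLT definition in three places (Grade 3 IRRs, Grade 3 ALT/AST laboratory values, Grade 4 cytopenia duration) without saying why

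*SAP*

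**What the plan says.** Protocol 8.2 gives the DLT definition and extends it beyond Cycle 1: "Related TEAEs meeting DLT definitions occurring in later cycles or in Phase 2 (DLT-like events) will determine the suitability of the MTD/OBD dose". Three of its elements matter here.

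- A Grade 3 IRR is exempt only under two conditions: "Grade 3 IRR that responds to symptomatic treatment, without recurrence of Grade 3 symptoms".
- ALT and AST have their own exemption: "Grade 3 elevation of alanine aminotransferase (ALT) or aspartate aminotransferase (AST) that resolves to Grade ≤1 or baseline within 7 days".
- Cytopenias count by duration: "Grade 4 neutropenia lasting more than 7 consecutive days" and "Grade 4 thrombocytopenia lasting more than 14 consecutive days".

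SAP Appendix C prints this text in one column and the algorithm in the next.

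- **Item 1e** defines the IRR exception as the IRR flag set and the grade equal to 3. It covers IRR events and their signs and symptoms.
- **Item 1d** keeps the 7-day ALT/AST exemption for AE records. Item 1a(1) separately counts every Grade 3 or higher creatinine, BUN, bilirubin, ALT or AST laboratory result that was not already abnormal at baseline.
- **Items 2b and 2c** are marked not applicable and sent to 2e. There a Grade 4 platelet or neutrophil record is kept if it does not "return to the following prior to or including the next scheduled dose date (use exposure dates for this"), the targets being platelets of at least 50 and neutrophils of at least 1 × 10⁹/L. The date is defined as: "Scheduled dose date = date the next dose should have occurred, e.g. schedule D would be 28 days after the previous dose".

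The change log in SAP 7.14 says only that the algorithms were added to give derivation detail. The assumptions at the end of Appendix C do not address these three points.

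**The concern.** DLT-like frequency is a secondary endpoint of Parts 1 and 2 (Protocol 5.4.1.2 and 5.4.2.2), and the protocol gives it a purpose: judging whether the MTD/OBD suits future studies. Appendix C reads as an implementation of Protocol 8.2, not as a modified definition. A report that followed it exactly would show, under the protocol's name, a count that the protocol does not define.

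The IRR category is not empty in this study. One of the two DLTs at 6 mg/kg every 4 weeks was a Grade 3 IRR (Protocol 4.6.2). Table 8.h in Protocol 8.7.1.1.2 provides for Grade 3 reactions that persist ("If the intensity of the IRR remains at Grade 3 after 2 hours") or come back, up to a third time. Those are the reactions that Protocol 8.2 does not exempt.

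SAP 7.12.1 summarizes by schedule, while the cytopenia window in 2e changes with the schedule. Part of any difference between schedules would therefore come from the rule.

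**Working it through.** The point concerns definitions, so there is no planned figure to reproduce. I set the rules side by side and ran illustrative courses through both.

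**1. Grade 3 IRR.** Protocol exemption: responds to treatment AND no Grade 3 recurrence. SAP exemption: flagged AND Grade 3.

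| Course of a related Grade 3 IRR | Protocol 8.2 | SAP 1e |
|---|---|---|
| Responds, no recurrence | exempt | removed |
| Responds, Grade 3 recurs | counts | removed |
| Does not respond | counts | removed |

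The last two rows can return only through item 3, which takes any related TEAE with the next dose delayed more than 14 days. Grade 4 IRRs are still counted. This departure undercounts.

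**2. Grade 3 ALT/AST.** Take a rise from normal baseline that resolves in 5 days. Since 5 ≤ 7, it is exempt under Protocol 8.2, and 1d removes the AE record. The laboratory value behind it is counted under 1a(1). The episode re-enters, against both the protocol and the SAP's own 1d. The 72-hour laboratory exemption in Protocol 8.2 does leave out hepatic values, but ALT/AST has the separate 7-day exemption. This departure overcounts.

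**3. Grade 4 cytopenia.** Intervals are from Protocol 6.1. With a dose on Day 1, the next is due on Day 1 + interval. If Grade 4 starts on Day 2, the longest Grade 4 run left uncounted is max(0, interval − 1 − lag). The lag is the time from the last Grade 4 day to the 2e threshold. Its length is not in the documents, so I show 0 (an upper bound) and an assumed 7 days.

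| Schedule | Interval | Next dose | Lag 0 | Lag 7 |
|---|---|---|---|---|
| A, weekly phase | 7 | D8 | 6 | 0 |
| B; A Cycles 3–6 | 14 | D15 | 13 | 6 |
| C | 21 | D22 | 20 | 13 |
| D; A from Cycle 7 | 28 | D29 | 27 | 20 |

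Against the protocol's more than 7 days (ANC) and more than 14 days (platelets), the runs that can be missed (lag 0 / lag 7) are:

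- Weekly A: none.
- B and A Cycles 3–6: ANC 8–13 / none; platelets none.
- C: ANC 8–20 / 8–13; platelets 15–20 / none.
- D and A from Cycle 7: ANC 8–27 / 8–20; platelets 15–27 / 15–20.

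Assumed true courses, each with a sample taken during Grade 4:

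| Course | Protocol | SAP 2e |
|---|---|---|
| (a) ANC Grade 4 D8–15 (8 days), ≥1 on D22 | yes | B yes; C, D no |
| (b) ANC Grade 4 D7–10 (4 days), ≥1 only on D22 | no | B yes; C, D no |
| (c) Platelets Grade 4 D8–22 (15 days), ≥50 on D29 | yes | D no |
| (d) ANC Grade 4 D21–23 (3 days), still <1 on D29 | no | D yes |

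The error goes both ways, and in (a) and (b) one course is classified differently by schedule. Protocol 4.6.2 reports Grade 4 neutropenia at 30% and Grade 4 thrombocytopenia at 17%. These are incidences without durations and are not limited to later cycles, so they cannot be turned into a number of misclassified patients.

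**The case against.** The best defence concerns 2e. Both of its thresholds are the retreatment levels in Protocol 8.4.2 (ANC 1000/mm³, platelets 50,000/mm³), and its time point is when the next dose is due. It is a traceable operational rule that can be computed in every cycle. The protocol's durations often cannot. From Cycle 3, scheduled hematology is on Days 1 and 15 only for B and for A Cycles 3–6, and on Day 1 only for C, D and A from Cycle 7 (Appendix A). Counting consecutive weekly samples in Cycle 2 does not solve this. With ±2-day visit windows, samples nominally on D8 and D15 can span D10–13 (4 days), and three samples D10–20 (11 days). G-CSF may also be used to reach the ANC level, so continuity between samples is a weak assumption. This defence stands, and it makes replacing 2e outright a trade-off. It does not excuse leaving the surrogate undeclared, and it does not touch 1e or 1a(1).

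The second defence is small consequence. The endpoint is descriptive. Grade 3 or higher AESIs, Grade 3 and 4 TEAEs, dose delays, and platelet and ANC profiles are reported separately (SAP 7.12.1, 7.12.2). Within one dosing interval the 2e window is the same at every dose. All of this is true. The events stay visible, but this endpoint's own count would still be wrong.

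Some stronger readings are not supported:

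- A reader might infer that no Grade 3 IRR can ever be counted; item 3 remains open.
- A reader might infer that the MTD or the Part 3 doses rest on these counts. Cycle 1 DLTs are identified by the investigator (SAP 7.12.1), and the MTD is already stated in the protocol.
- A reader might infer that the laboratory route breaks the relatedness requirement. Assumption 2 speaks of TEAEs and does not say how it applies to laboratory records, so that needs only a clarifying sentence.

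**Conclusion.** The point holds in this form: Appendix C is presented as Protocol 8.2 but differs from it in three places with no stated reason. Item 1e removes Grade 3 IRRs that the protocol would count, unless item 3 recovers them. Item 1a(1) brings back ALT/AST episodes that the protocol exempts. Item 2e substitutes non-recovery by the next dose for a duration, with a window of 7 to 28 days. The first two follow from the text alone. The day ranges for the third rest on an assumed Day 2 onset and on the lag shown; the lag-0 column is an upper bound.

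The net effect on the counts, and even its sign, cannot be obtained from the documents. The reach is one descriptive secondary safety endpoint in Parts 1 and 2. Cycle 1 DLTs, the MTD and Part 3 are outside it. It should be corrected, because the protocol uses this endpoint to judge dose suitability and the correction is small.

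**What to change.** - **Item 1e:** exclude only Grade 3 IRRs that meet both Protocol 8.2 conditions on the available eCRF data, and list those that cannot be judged.
- **Item 1a(1):** apply the 7-day ALT/AST exemption to Grade 3 laboratory values, as 1d already does for AE records.
- **Item 2e:** keep it, but label its output as a surrogate for the Protocol 8.2 duration criteria, state the reason, and do not report it as the protocol-defined event. Where actual sample dates or AE dates allow, also report episodes meeting the more-than-7-day and more-than-14-day criteria, with the number not evaluable. Use actual dates, not nominal visit days.

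The cost is one appendix and one derivation to revise. Counts may move either way. Some IRRs will not be classifiable, because what the eCRF captures depends on completion guidelines that are not in the documents (Protocol 8.7.1.1). Many cytopenia episodes from Cycle 3 will not be evaluable for duration. AE dates will fill only part of that gap, since Protocol 10.1.2 makes an abnormal laboratory value an AE only under stated conditions.
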